16.1.5.3. Analysis of dose-response

A supplementary analysis of the primary efficacy of SEP-4199 will be conducted on the ITT population to explore the dose response relationship using the generalized Multiple Comparison Procedure – Modeling (gMCP-Mod) methodology (Pinheiro 2014).

The gMCP-Mod approach to dose response will be implemented using R software, in particular the DoseFinding package ([APPENDIX 3](#)).

First, to obtain estimates of the dose response, an MMRM model on the ITT population with factors for treatment dose level, region, week, and baseline MADRS score as a continuous covariate will be used to model the change from baseline in MADRS score over time from the placebo and SEP-4199 groups. The LS mean of change from baseline in the MADRS total score at Week 6 for each SEP-4199 group and placebo and the corresponding variance-covariance matrix will be obtained from the model.

Next, the gMCP-Mod approach will use the estimates obtained from the MMRM model to analyze the dose response relationship at Week 6. The following set of candidate models for the dose response relationship will be considered ([APPENDIX 3](#)), but in case of inability to correctly fit data, a model could be removed from the analyses:

- Linear model (no parameters)
- Quadratic model (δ)
- E_{max} model (ED_{50})
- Sigmoidal E_{max} (ED_{50} , h)

Once a set of candidates are identified, the selection will be made using the MCPMod function from DoseFinding R package. The null hypothesis of a constant dose-response curve for the primary endpoint will be tested at the significance level of 5% against the one-sided alternative hypothesis of a non-constant dose response curve using the gMCP-Mod methodology.

For each of the dose-response models in the candidate set, the null hypothesis that the sum of the components of the optimal contrast vector is equal to zero will be tested. To do so, the contrast coefficients of each model are chosen so they maximize the power to detect the absence of dose response.

Under the null hypothesis, the vector of the optimal contrasts for the candidate models follows

Document:

Author:

Version Number:

V2.0

Version Date:

21MAY2020

Template No: CS_TP_BS016 Revision 4
Effective Date: 01Apr2016

Reference: CS_WI_BS005

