asymptotically normal distribution. If the maximum asymptotic z statistic for the model contrast tests exceeds the critical value (corresponding to a unilateral test with alpha = 0.05), then the null hypothesis will be rejected and the proof of concept of a non null dose-response will be demonstrated.

The final detection of a significant dose-response signal is based on the adjusted p-value of the contrast test statistic. If no model contrast is significant (could be due to small sample size, high variance within the data, choice of candidate models, etc.), no dose response relationship will be further explored. Otherwise, the models with significant adjusted p-values will be selected for further investigation. The best/optimal model will be the one with the minimum Akaike Information Criterion (AIC) criterion. AIC for each model will be displayed in the table and the optimal model with the minimum AIC will be indicated.

The target dose of interest is the minimum effective dose (MED) level that will achieve a target effect of delta over placebo effect. The target dose of interest will be estimated using each significant model using inverse regression techniques. The target dose will be computed on both continuous and discrete scales using R software. Effective dose (ED_p), the dose level that achieves a certain percentage p of the maximum effect over placebo (ie, ED_{10} , ED_{25} , ED_{50} , ED_{75} , ED_{90}) will also be calculated on both continuous and discrete scales.

Alternatively, a weighted average of the significant model contrasts will also be used to calculate a weighted average of the estimated target dose.

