The E_{\max} model is used to represent monotone, concave dose-response shapes. To distinguish it from the more general sigmoid E_{\max} model it is sometimes also called hyperbolic E_{\max} model. For the E_{\max} model, there is one parameter ED_{50} to be estimated.

- Sigmoidal E_{\max} : $f(d, \theta) = E_0 + E_{\max} d^h / (ED_{50}^h + d^h)$

The sigmoid E_{\max} model is an extension of the (hyperbolic) E_{\max} model by introducing an additional parameter h , that determines the steepness of the curve at the ED_{50} value. The sigmoid E_{\max} model describes monotonic, sigmoid dose-response relationships. For the Sigmoid E_{\max} model, there are two parameters ED_{50} and h to be estimated.

The next step is to determine the initial values of model parameters for the candidate models. Initial values for standardized model parameters can be calculated based on observed value at Week 6..

```
fitlinear<- fitMod(dose=dose, resp= resp, data = xxx, model="linear")
fitquadratic<- fitMod(dose=dose, resp= resp, data = xxx, model="quadratic")
fitemax<- fitMod(dose=dose, resp=resp, data = xxx, model="emax")
fitsigemax<- fitMod(dose=dose, resp=resp, data = xxx, model="sigEmax")
```

Note: Dose is 0 for placebo, 200 for SEP-4199 200mg/day and 400 for SEP-4199 400mg/day. Resp is the response so change from baseline at Week 6 in MADRS Total Score.

Document:

Author:

Version Number:

V2.0

Version Date:

21MAY2020

Template No: CS_TP_BS016 Revision 4
Effective Date: 01Apr2016

Reference: CS_WI_BS005

Based on an estimate of the dose-response vector and its associate variance/covariance matrix, optimal contrast will be computed for each model to maximize the power to test the null hypothesis of a constant dose-response curve. To obtain this estimate, an MMRM model with factors for treatment dose level, region, week, and baseline MADRS score as a continuous covariate will be used to model the change from baseline in MADRS score over time from the placebo and SEP-4199 groups for the ITT population. This analysis can be performed using the SAS software ([Dmitrienko, 2017](#)).

```

PROC MIXED;
  CLASS SUBJID REGION TRTPN WEEK;
  MODEL TOTCFB = TOTBL REGION TRTPN WEEK TRTP*WEEK / DDFM=KR RESIDUAL;
  REPEATED WEEK/TYPE=UN SUBJECT=SUBJID;
  LSMEANS TRTPN*WEEK /PDIFF CL COV;
  *ODS OUTPUT LSMEANS=MUH (KEEP=TRTPN WEEK ESTIMATE);
  *ODS OUTPUT LSMEANS=COVH (KEEP=TRTPN WEEK COVx COVy COVz) ;
RUN;

```

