After a dose response signal is established in the first step, one proceeds to the Mod step, fitting the dose response profile and estimating target doses based on the models identified in the MCP step (Pinheiro 2014). The candidate models will be retained to fit the data. The Generalized AIC (gAIC) will be used to select the model for which the maximum likelihood fit provides the smallest gAIC value. The fitMod function in DoseFinding can be used for this analysis.

If at least one significant model is found in Step 1 then use following code:

```
ModStep=MCPMod(doses, muH, S=covH, models=mod, type = "general", doseType="TD", Delta=3.5, pVal = T)
```

If no significant model is found in Step 1 then use following code:

```
ModStepEM <- fitMod(doses, muH, S=covH, model="emax", type = "general")
gAIC(ModStepEM)
coef(ModStepEM)
plot(ModStepEM)
```

```
ModStepQ <- fitMod(doses, muH, S=covH, model="quadratic", type = "general")
gAIC(ModStepQ)
coef(ModStepQ)
plot(ModStepQ)
```

```
ModStepLin <- fitMod(doses, muH, S=covH, model="linear", type = "general")
gAIC(ModStepLin)
coef(ModStepLin)
plot(ModStepLin)
```

```
ModStepsigEM <- fitMod(doses, muH, S=covH, model="sigEmax", type = "general")
gAIC(ModStepsigEM)
coef(ModStepsigEM)
plot(ModStepsigEM)
```

Document:

Author:

Version Number:
Version Date:

V2.0
21MAY2020

Template No: CS_TP_BS016 Revision 4
Effective Date: 01Apr2016

Reference: CS_WI_BS005

Estimation of target doses is done based on the selected fitted model for the dose response parameter ([Bornkamp 2009](#)).

TD(ModStep, Delta=xxx, direction="decreasing")

TD(ModStep, Delta=xxx, TDtype = "discrete", doses=doses, direction="decreasing")

Note: Appropriate Delta will be explored based on results

ED(ModStep, p=0.5)

ED(ModStep, p=0.5, EDtype = "discrete", doses=doses)

Note: Repeat for 10%, 25%, 50%, 75% and 90%

Alternatively, model averaging approaches can be used to avoid the need to select a single model. The individual AIC values for the candidate models with significant contrast test statistics determine the model averaging weights ([Buckland 1997](#)). This applies both to dose response and target dose estimation ([Pinheiro 2014](#)).

MM2 <- MCPMod(doses, muH, S=covH, type = "general", models=mod, alpha = 0.05, Delta=xxx, selModel = "aveAIC", doseType = "TD", alternative = "one.sided")

Note: Appropriate Delta will be explored based on results

TDEst <- MM2\$doseEst%*%MM2\$selMod

TDEst

PK ANALYSIS

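### The MCP-Mod step fits a four-parameter sigmoid Emax to three dose means, lets AIC name a best curve where quadratic and Emax tie, and gives two different instructions for the MED margin

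*SAP*

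**What the plan says.** SAP 16.1.5.3 takes its input from an MMRM: the three arms' adjusted Week 6 means of the MADRS change, with their covariance matrix. Appendix 3 states the doses: "Dose is 0 for placebo, 200 for SEP-4199 200mg/day and 400 for SEP-4199 400mg/day". The candidate shapes are linear, quadratic, Emax and sigmoid Emax. For sigmoid Emax, Appendix 3 says "there are two parameters ED_{50} and h to be estimated", in addition to E0 and Emax.

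Among models with a significant contrast, "The best/optimal model will be the one with the minimum Akaike Information Criterion (AIC) criterion". Section 16.1.5.3 also asks for the target dose from each significant model, for ED10 to ED90, and for a weighted average of target doses. On the average, Appendix 3 says "The individual AIC values for the candidate models with significant contrast test statistics determine the model averaging weights". One escape clause is given: "in case of inability to correctly fit data, a model could be removed from the analyses".

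Section 16.1.5.3 defines the MED through a margin delta but gives no value. In Appendix 3 the main `MCPMod` call has `Delta=3.5`. The `TD` and model-averaging calls have `Delta=xxx`, with the note "Appropriate Delta will be explored based on results".

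The Protocol (synopsis and 15.3.5.1.2) names the same four possible shapes and the minimum-AIC rule, and calls the analysis supplementary.

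**The concern.** Three means carry three pieces of information. A curve with four free parameters cannot be estimated from them, and two different three-parameter curves can each pass through all three points. The plan would nevertheless report doses read off the four-parameter curve, give that curve a weight in an average, and label one curve as best.

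At stake is what the report says about the shape between the studied doses and about the minimum effective dose. A target dose from sigmoid Emax would look like an estimate although the data do not determine it. An MED also depends directly on Delta, so two instructions for Delta can lead to two reported MEDs.

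**Working it through.** **Inputs.** Doses 0, 200 and 400 mg and the model formulas (SAP Appendix 3). 93 evaluable subjects per arm, SD 8.745, difference 3.85 (SAP 3.4). Scenario 1 has effect sizes 0.44/0.44 and Scenario 2 has 0.22/0.44 (SAP Appendix 4), that is 3.85/3.85 and 1.925/3.85 points. Effects are written as positive improvements over placebo. The 3.0/4.2 example and the range of h are assumptions.

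**The plan's own figures.** The documents give none for the MCP-Mod step. As a check on the inputs, the primary power was re-simulated (z version): at least one rejection 0.905 (SAP Table 8: 0.9027), both 0.752 (0.7517).

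**1. Parameter count against three means.** Linear 2, quadratic 3, Emax 3, sigmoid Emax 4. The Jacobian of sigmoid Emax at 0/200/400 has rank 3 of 4.

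**2. What sigmoid Emax leaves open.** Let R = effect at 400 / effect at 200. Solving the formula at both doses gives ED50^h = (R − 1)·400^h / (2^h − R), with Emax = e(400)·(ED50^h + 400^h)/400^h. For effects 3.0 and 4.2, R = 1.4, and an exact solution exists for every h with 2^h > 1.4.

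Check at h = 1: ED50 = 0.4 × 400/0.6 = 266.7. Emax = 4.2 × 666.7/400 = 7.0. Effect at 200 = 7 × 200/466.7 = 3.0. Dose for Delta = 2 is 266.7 × 2/(7 − 2) = 106.7 mg.

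| h | ED50 (mg) | dose for Delta = 2 | dose for Delta = 3.5 | dose for 10% of the 400 mg effect |
|---|---|---|---|---|
| 0.7 | 913 | 96 | 271 | 8 |
| 1 | 267 | 107 | 267 | 17 |
| 2.4 | 155 | 138 | 248 | 59 |
| 5 | 168 | 164 | 228 | 108 |
| 10 | 183 | 181 | 214 | 147 |

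Every row reproduces both effects exactly. With effects 3.0/3.85 and h from 1 to 10, the Delta = 2 dose runs from 94 to 178 mg.

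**3. How often this arises.** An exact sigmoid fit needs 0 < effect at 200 < effect at 400. The SE of a difference is 8.745 × √(2/93) = 1.282. In Scenario 2 each step is 1.925 (z = 1.50, failure probability 0.067), so about 1 − 2 × 0.067 = 87% of trials. In Scenario 1 the second step is zero, so about 50%.

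**4. AIC.** Take AIC as weighted residual sum of squares plus 2 per parameter, with independent means of variance SD²/93.
- Quadratic always scores 6.
- Emax has effect ratio 200/400 equal to (ED50 + 400)/(2(ED50 + 200)), which lies between 0.5 and 1. Inside that range (down to about 0.63 if ED50 is capped at 600 mg) it also scores 6, an exact tie.
- Sigmoid Emax scores at least 8.
- Linear scores 4 plus a 1-df lack-of-fit term, so it beats quadratic when that term is below 2. The variance of m0 − 2·m200 + m400 is 6 × 8.745²/93 = 4.93, SD 2.22. In Scenario 1 the true contrast is 3.85, or 1.73 SDs, so P(linear) = Φ(1.41 − 1.73) − Φ(−1.41 − 1.73) ≈ 0.37. In Scenario 2 it is zero, so P(linear) = 2Φ(1.41) − 1 ≈ 0.84.

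Simulation limited to trials with a best z above 1.645, ED50 bounded at 0.4 to 600 mg:

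| Scenario | linear lowest | exact quadratic/Emax tie | quadratic lowest, Emax within 2 units | quadratic clearly lowest |
|---|---|---|---|---|
| 1 | 36% | 16% | 39% | 8% |
| 2 | 84% | 4% | 4% | 8% |

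**5. Averaging weight.** When all three curves fit exactly, the sigmoid weight relative to quadratic or Emax is e^(−(8−6)/2) = e^−1, whatever the data. Its share is e^−1/(2 + e^−1) = 15.5% if linear is not in the average, and e^−1/(2 + e^−1 + e) = 7.2% if linear fits perfectly.

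**6. Delta.** In the 3.0/4.2 example the MED on the discrete scale is 200 mg at Delta = 3.0 and 400 mg at Delta = 3.5. The margin alone decides which studied dose is named.

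**The case against.** The strongest reply is that this is a supplementary, exploratory analysis with no hypothesis or Type I error attached, and that much of it is already protected. Several parts of that reply stand.

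- A reader might infer that the whole AIC step is arbitrary. It is not. Linear keeps one residual degree of freedom, so linear versus curved is a real comparison.
- A reader might infer that sigmoid Emax could be declared best. While quadratic is eligible it cannot be, since it scores at least 8 against 6.
- Exact sigmoid fits are not universal. In about half of Scenario 1 trials the observed effect does not rise from 200 to 400 mg, and the family in the first table does not arise.
- Discrete-scale target doses do not depend on (ED50, h), because all exact-fit curves agree at the studied doses. The plan also already reports AIC and target doses by model.
- A reader might infer that the margin is wholly post hoc. The main call fixes 3.5, so the defect is a conflict between calls. The documents do not support any suggestion about intent.
- Doses between 0 and 200 mg are interpolation, since placebo is in the fit.
- The documents do not say that the MED will be used for later development, only that it will be explored.

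The removal clause could be read to cover a model that is not identifiable. But it speaks of failure to fit and gives no criterion. A curve that passes through every mean does not clearly trigger it.

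**Conclusion.** The point holds within limits. Followed as written, the plan yields continuous-scale target doses and EDp values from sigmoid Emax that the data cannot determine. In the example, the Delta = 2 dose spans 96 to 181 mg and the 10% dose 8 to 147 mg. The model's averaging weight relative to the saturated curves is fixed by its parameter count. AIC cannot say which of quadratic and Emax is best when both fit exactly. The Delta instructions contradict each other.

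The example effects and the range of h are illustrative; the parameter count and the tie do not depend on them. The percentages rest on the SAP's scenarios, independent means, the assumed ED50 bounds and the simple significance screen. The consequence is confined to this supplementary analysis: the primary comparison and its error control are untouched.

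**What to change.** Before unblinding:

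1. Drop sigmoid Emax from fitting, selection, target-dose estimation and averaging. Alternatively, keep it only as a contrast with ED50 and h fixed in advance, not taken from the Week 6 data as Appendix 3 now does.
2. Use AIC for linear versus curved only. When quadratic and Emax tie, call neither best and present both target doses.
3. Use one pre-specified Delta in every MED call. The SAP already codes 3.5. Label results at any other value exploratory.
4. Label continuous target doses between studied doses as model-dependent interpolation.
5. List these changes under SAP 3.7, because the four shapes and the minimum-AIC rule are also Protocol text.

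The cost is SAP and R-code wording plus the 3.7 entry. The downside is one fewer shape in an exploratory analysis. No information is lost, because three means carry none about a fourth parameter.

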16.1.6. SUBGROUP ANALYSIS OF PRIMARY EFFICACY VARIABLE

For each of the subgroup factors listed in [Section 7.5](#), change from baseline in MADRS score at Week 6 will be analyzed using the same MMRM method with additional terms for the subgroup, subgroup-by-treatment interaction, subgroup-by-visit interaction, and subgroup-by-treatment-by-visit interaction using the ITT population. The MMRM with the additional by region subgroup interaction terms will be repeated after removal of all assessments conducted during remote visits and also by only keeping the records reported before 11 March 2020 separately. For country analysis, region will be replaced by country in the model. Summary statistics, LS mean treatment differences (each SEP-4199 group minus placebo), and effect size of change from baseline by week, their 2-sided 95% CIs, and the associated p-values will be provided as well as the p-value for the treatment-by-subgroup interaction. Its statistical significance will be assessed at the 0.10 level for homogeneity of the treatment effect across the different categories of a subgroup factor. In case a significant interaction effect is detected, estimates by subgroup will be examined to determine the nature of the interaction (qualitative or quantitative).

For these subgroups, a forest plot will be produced.

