15.3.5.5. Efficacy Subgroup Analyses

Subgroups, including but not limited to country, gender (male, female), race (White and Non-white for the statistical model, the rest of categories, Black/African American, Asian, American Indian/Alaskan Native, Native Hawaiian/Pacific Islander, Other, will also be summarized), ethnicity (Hispanic and non-Hispanic), age groups, and bipolar I diagnosis subtype (rapid cycling and non-rapid cycling) will be detailed in the SAP. For the primary and the secondary efficacy endpoints, analysis will be performed for the subgroups with the same MMRM with additional terms for the subgroup, subgroup-by-treatment interaction, subgroup by visit interaction and subgroup-by-treatment-by visit interaction using the ITT population. For the country analyses, region will be replaced with country. Summary statistics and the LS mean treatment differences (each SEP-4199 group minus placebo) of change from baseline at Week 6, their 2-sided 95% CIs, and the associated p-values will be provided as well as the p-value for the treatment-by-subgroup interaction.

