16.1.1. PRIMARY EFFICACY VARIABLE & DERIVATION

The primary efficacy endpoint is the change from baseline in the MADRS total score at Week 6.

The MADRS is a clinician-rated assessment of the subject's level of depression. The measure contains 10 items that measure apparent and reported sadness, inner tension, reduced sleep and appetite, difficulty concentrating, lassitude, inability to feel, and pessimistic and suicidal thoughts. Each item is scored in a range of 0 to 6 points, with higher scores indicating increased depressive symptoms. Total

Document:

Author:

Version Number:

V2.0

Version Date:

21MAY2020

Template No: CS_TP_BS016 Revision 4
Effective Date: 01Apr2016

Reference: CS_WI_BS005

score will be equal to the sum of the 10 items (range between 0 and 60). MADRS is assessed at Visit 1/Screening, Visit 2/Baseline/Week 0, Visit 3/Week1, Visit 4/Week 2, Visit 5/Week 4, and Visit 6/Week 6.

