APPENDIX 3. STATISTICAL MODEL SPECIFICATIONS

MIXED MODEL FOR REPEATED MEASURES (MMRM)

Ods graphics on;

```
PROC MIXED DATA=XXX plots=(studentpanel(marginal) pearsonpanel(marginal));
```

```
  CLASS SUBJID REGION TRTPN WEEK;  
  MODEL TOTCFB = TOTBL REGION TRTPN WEEK TRTPN*WEEK / DDFM=KR RESIDUAL OUTPM=OUTRESIDUAL;  
  REPEATED WEEK/TYPE=UN SUBJECT=SUBJID;  
  LSMEANS TRTPN*WEEK /PDIFF CL;
```

RUN;

*Where WEEK = Week 1, Week 2, Week 4, Week 6;

Ods graphics off;

In case the MMRM model assuming the unstructured covariance variance structure fails to converge, the spatial exponential or spatial power covariance structure will be assumed sequentially along with a robust sandwich estimator. The first covariance structure to yield convergence will be used in the analysis.

```
PROC MIXED EMPIRICAL;
```

```
  CLASS SUBJID REGION TRTPN WEEK;  
  MODEL TOTCFB = TOTBL REGION TRTPN WEEK TRTPN*WEEK / RESIDUAL OUTP=OUTRESIDUAL;  
  REPEATED WEEK/TYPE=SP(EXP) (WEEK) SUBJECT=SUBJID;  
  REPEATED WEEK/TYPE=SP(POW) (WEEK) SUBJECT=SUBJID;  
  LSMEANS TRTPN*WEEK /PDIFF CL COV;
```

RUN;

*EMPIRICAL IS FOR THE SANDWICH ESTIMATOR;

Within-group effect size will be calculated as the absolute value of LS mean of change from baseline divided by SD, obtained as the SE of the LS Mean multiplied by the square root of the treatment group change from baseline sample size at each visit. Between-group effect size at a visit will be calculated as the absolute value of the LS means difference from Placebo divided by the model estimate of the pooled SD at the visit, which is obtained from the square root of the diagonal element, associated at the visit, from the covariance matrix (R matrix of subjects with MADRS total score at all visits). Although the variance-covariance estimates are calculated differently depending on the covariance structure being applied for the model, the diagonal of the R matrix will contain the variance estimate at each visit that can be used for the effect size calculations regardless of the covariance structure.

Document:

Author:

Version Number:

V2.0

Version Date:

21MAY2020

Template No: CS_TP_BS016 Revision 4
Effective Date: 01Apr2016

Reference: CS_WI_BS005

For All SEP-4199 column for safety questionnaires:

- LS Means estimate, 95%CI and SE is obtained using following statements:

```
LSMESTIMATE TRT01PN*AVISITN "MEAN(200MG+400MG) at Week 1" [1, 1 1] [1, 2 1] / CL divisor=2;  

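### The subgroup interaction p-value is not tied to Week 6: taken by default from the named model term, it averages the treatment effect over Weeks 1, 2, 4 and 6

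*SAP*

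**What the plan says.** SAP 16.1.6 takes the primary MMRM and extends it "with additional terms for the subgroup, subgroup-by-treatment interaction, subgroup-by-visit interaction, and subgroup-by-treatment-by-visit interaction using the ITT population". It then asks for LS mean differences, effect sizes, confidence intervals and p-values by week within subgroups, "as well as the p-value for the treatment-by-subgroup interaction" (one per subgroup factor), and a forest plot. The rule for that p-value is: "Its statistical significance will be assessed at the 0.10 level for homogeneity of the treatment effect across the different categories of a subgroup factor". What follows a positive result is: "In case a significant interaction effect is detected, estimates by subgroup will be examined to determine the nature of the interaction (qualitative or quantitative").

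Protocol 15.3.5.5 has the same model. It lists Week 6 differences and their intervals, and then says that "the associated p-values will be provided as well as the p-value for the treatment-by-subgroup interaction". The protocol sets no 0.10 threshold. SAP 16.2.6 carries the method over to CGI-BP-S.

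The time point of interest is stated in SAP 16.1.1: "The primary efficacy endpoint is the change from baseline in the MADRS total score at Week 6". Hypotheses H1 and H2 and the estimand summary in SAP 16.1.3 are also at Week 6. In the Appendix 3 code, week is a class variable with four levels: "Where WEEK = Week 1, Week 2, Week 4, Week 6". That appendix covers the main MMRM but gives no subgroup model and no interaction contrast.

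**The concern.** In a model that contains the three-way term, the test of the two-way treatment-by-subgroup term does not refer to any one visit. By default in PROC MIXED it compares subgroups on the treatment effect averaged with equal weight over Weeks 1, 2, 4 and 6. A programmer who takes the p-value for the term the plan names will therefore judge homogeneity of that average, not of the Week 6 effect.

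This can mislead in two ways. A subgroup difference that emerges towards Week 6 is diluted by the early visits, and a non-significant p-value may then be reported as a consistent Week 6 effect. An early, transient difference can cross the 0.10 line although nothing remains at Week 6. Region is one of the factors, and SAP 16.1.6 reruns the region model without remote visits and with records before 11 March 2020 only, so the same p-value may be read several times.

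**Working it through.** **Inputs from the documents.** Four visits (Appendix 3). SAP 3.4 gives 93 evaluable subjects per arm, SD 8.745 and a planned difference of 3.85. The plan states no operating characteristic for the subgroup test, so there is no figure to reproduce for it. The borrowed inputs are consistent: 3.85/8.745 = 0.440, the stated effect size. Simulating the truncated Hochberg procedure (γ = 0.9) with 93 per arm gives 90.5% power for at least one comparison and 75.3% for both, against about 90% and 75% stated.

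**Step 1: what the two-way term tests.** A saturated 3 × 2 × 4 layout (treatment, subgroup, visit) with arbitrary cell means was coded sum-to-zero. The two-way coefficients were 0.0164 and 0.3252. The interaction computed from cell means averaged equally over the four visits was also 0.0164 and 0.3252. So the tested quantity is the equal-weight visit average.

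**Step 2: how much of a Week 6 difference enters.** The documents give no time course. Assumed profiles, as fractions of the Week 6 subgroup difference at Weeks 1, 2, 4 and 6:
- A (0.25, 0.50, 0.80, 1): mean 2.55/4 = 0.6375
- B (0, 0.25, 0.60, 1): mean 1.85/4 = 0.4625
- C (0, 0, 0.50, 1): mean 1.50/4 = 0.375
- D, constant: mean 1

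**Step 3: standardized difference relative to a Week 6 test.** Ratio = mean fraction ÷ (SD of the four-visit mean / Week 6 SD). With equal SDs and correlation 0.6 (assumed), the SD ratio is √[(1 + 3 × 0.6)/4] = √0.7 = 0.837. With visit SDs 0.60, 0.75, 0.90 and 1.00 of Week 6 (assumed) and the same correlation, the sum of squares is 2.7325 and the square of the sum is 10.5625. The variance of the mean is [2.7325 + 0.6 × (10.5625 − 2.7325)]/16 = 0.464, so the SD ratio is 0.681.

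| Profile | Equal SDs | Smaller early SDs |
|---|---|---|
| A | 0.76 | 0.94 |
| B | 0.55 | 0.68 |
| C | 0.45 | 0.55 |
| D | 1.20 | 1.47 |

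**Step 4: power of the 0.10 rule.** Assumptions: two-level subgroup split 50:50 (46.5 per arm per level), SD 8.745 at every visit, complete data, the same interaction Δ for both doses, 2-df chi-square test with critical value 4.605. For Week 6 the noncentrality is λ = Δ² × (2/3) / [8.745² × (1/46.5 + 1/46.5)]. For Δ = 3.85, λ = 14.82 × 0.667/3.289 = 3.00, power 44%. For Δ = 7.7, λ = 12.02, power 93%. For the averaged test, Δ is multiplied by the mean fraction and the variance by that of the visit mean. Ranges are over exchangeable correlation 0.5 to 0.7 and an autoregressive structure of 0.85 per week.

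| Time course | Averaged test, Δ = 3.85 | Averaged test, Δ = 7.7 |
|---|---|---|
| Week 6 test, for comparison | 44% | 93% |
| Linear in week, fraction (1/6 + 2/6 + 4/6 + 1)/4 = 0.54 | 23–27% | 59–68% |
| Late (profile C) | 16–18% | 36–41% |
| Constant | 53–61% | 98–99% |

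If a 7.7-point difference is present at Weeks 1, 2 and 4 and zero at Week 6, the averaged test is significant at 0.10 in 91% of trials (correlation 0.5), against 10% for the Week 6 test.

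**The case against.** The strongest reply is that the plan never says the p-value is the default test of the two-way term. SAP 16.1.6 opens by speaking of the Week 6 change, the protocol puts the interaction p-value at the end of a list of Week 6 quantities, and the main model is reported through treatment-by-week LS means rather than an averaged treatment effect. A Week 6 interaction may well have been meant. That stands as far as intent goes: a reader might infer that the SAP has expressly chosen an averaged test, and the text does not show that. But no contrast is written. Appendix 3 does write week-specific estimate statements for the pooled-dose safety comparisons, so the contrast is spelled out where it was thought necessary. If Week 6 was meant, the text still needs to say so.

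A reader might also infer that the 0.10 rule decides whether subgroup results are seen. It does not. Estimates by week and the forest plot are unconditional, and the rule only prompts a look at whether an interaction is qualitative or quantitative.

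Nor does averaging always cost power: with a constant difference it gains, and smaller early SDs soften the loss. The 7.7-point illustration is twice the planned treatment effect. All of this stands. The remaining objection is to the quantity tested, not to a uniform loss.

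**Conclusion.** The point holds as a low-severity improvement to an exploratory analysis. As written, with the named term and no contrast, the default p-value judges homogeneity of a four-visit average, while the endpoint, hypotheses and estimand are at Week 6. That it would be taken from the default test is an inference from the model terms and the software, not a statement in the SAP.

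The direction and size of the consequence depend on an unknown time course and on unknown visit SDs and correlations. The Step 3 ratios run from 0.45 (late difference, equal SDs) to 1.47 (constant difference, smaller early SDs), and a spurious flag is possible when an early difference fades.

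It would be wrong to read this as a threat to the trial's conclusions. The gatekeeping procedure in SAP 7.4 covers only H1 to H4, SAP 7.5 already warns of limited power within subgroups, and the success criterion in SAP 16.1.3 does not use this p-value.

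**What to change.** In SAP 16.1.6, define the interaction p-value as the treatment-by-subgroup contrast at Week 6, built from the subgroup-by-treatment-by-visit cell means and joint over both doses. That is 2 df for a two-level subgroup and 2 × (levels − 1) in general; for country in the US and Europe cohort, with the seven countries listed in SAP section 11, it is 2 × 6 = 12 df. Per-dose contrasts may be added as a supplement. Apply the 0.10 rule to the Week 6 contrast.

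Make the same change for CGI-BP-S through SAP 16.2.6, and add the subgroup model and contrast code to Appendix 3. The visit-averaged test can stay as a labelled supplement.

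The cost is one contrast statement per subgroup factor. The model and the data are unchanged.
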